6.4 Data Transformations and Derivations

- Age in years (round down) will be calculated using informed consent date and birth date.
- Time variables based on two dates (e.g., Start Date and End Date), will be calculated as (End Date Start Date) (in days) unless otherwise specified in the planned analysis section. For example, the postoperative day = postoperative visit date lens implantation date (i.e. surgical date).
- The following unit conversion will be implemented unless otherwise specified:
 - o Months = Days / 30.4375
 - o Years = Days / 365.25

6.5 Handling of Dropouts and Missing Data

All data analyses will be conducted based on available data. No imputation will be performed.

6.6 Examination of Subgroups

Due to possible subset of eyes implanted having underlying pathology resulting in poor preoperative BCDVA, separate analyses will be provided for effectiveness with this subset of eyes and the remaining eyes without poor preoperative BCDVA.

6.7 Covariates

Covariates are not considered for adjustment in the analyses.

6.8 Timing of Analyses

An interim analysis will be performed when all enrolled subjects either have been seen for their 4-6 month visit, or have earlier exited from the study before the 4-6 month visit, or the visit window has closed for the 4-6 month visit (i.e., missed visit).

Interim safety summaries will be provided for annual reports based on regulatory requirement. Postoperative follow-up through 12 months on all implanted subjects will be completed as per protocol at which the final report analysis will be performed.

7 PLANNED METHODS OF ANALYSES

7.1 Accountability and Disposition

Accountability of the eyes by visit will be provided based on ISO 11979-7:2014(E) for all eyes. Reasons for discontinuation of study will be summarized. The number and percentage of eyes and subjects in each analysis population will be summarized.

7.2 Demographic and Baseline Characteristics

Demographics, preoperative parameters, and operative parameters will be summarized descriptively by mean, standard deviation, median, minimum, and maximum for the continuous outcomes and by count and percentage for the categorical outcomes.

7.3 Protocol Deviations

Major protocol deviations are those that represent a divergence from the protocol that could have a significant effect on the integrity of the study data, or on the subject's rights, safety, or welfare. Major protocol deviations also include exemptions to the study inclusion/exclusion criteria and will be summarized by category. A list of subjects with major protocol deviations will be presented.

7.4 Effectiveness Analysis

7.4.1 Primary Analyses of the Primary Effectiveness Endpoint

The 4-6 month MRSE value of the primary eyes will be summarized descriptively by mean, standard deviation, median, minimum, and maximum based on the intended refractive target. MRSE stability (i.e., no change [±0.50 D]) within two consecutive postoperative visits at 1 month or later will be calculated.

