 - o No visible damage to either the PCIOL or the IOPCL
 - o Uniform leaflet coverage of all IOPCL haptic tabs
- Long-term adherence and positional stability
 - Minimal Change in uniformity of the gap between 1-2 months and 4-6-months as determined by UBM measurements. Minimal change is defined as +/- 10 microns between visits is established and maintained using UBM imaging
- Characterization and incidence of cumulative and persistent intraoperative and post-operative adverse events.

Stopping Rules

The Sponsor or the clinical investigator can suggest suspension of the clinical trial at any time if they are in receipt of information that leads them to believe that continuing the study jeopardizes the health and welfare of the clinical trial participants. Suspension of the study will be considered if two or more consecutive severe ocular injuries occur at any one clinical site that are related to the surgical procedure and/or IOPCL device. A severe ocular injury results in a permanent impairment of a vision or permanent damage to an eye.

Examples:

- Uveitis-Glaucoma-Hyphema (UGH) Syndrome. Intraocular chafing from the IOL/PCIOL implant leading to a spectrum of iris transillumination defects and pigmentary dispersion to microhyphemas with elevated intraocular pressure.
- Posterior capsule rupture with IOL/PCIOL dislocation resulting in a posterior vitrectomy during the surgical procedure

Primary Effectiveness Endpoint

Proportion of eyes ($\geq 50\%$) able to achieve a stable target refraction, (manifest or autorefraction) within 0.5 D of the intended target. Stability is achieved when there is no change (± 0.50 D) within two consecutive postoperative visits at 1 month or later visits.

04-08-2021 5

3. Subject Population

A maximum of 10 pseudophakic eyes will be implanted unilaterally with the AccuraSee IOPCL.

3.1. Inclusion Criteria:

- 1. Subjects who have already had cataract surgery with a Bausch and Lomb monofocal intraocular lens model LI61A0 (with lens power from 18.0 diopters (D) to 23.0 D) or model LI61SE (with a lens power from18.0 D to 22.5 D), as clearly evidenced by photographic documentation with one of the following: (1) patient medical record, (2) clinic chart with labeling attached, (3) surgical record with labeling attached, or (4) patient identification card with make, model, power, and serial number.
- 2. Able to comprehend and sign a statement of informed consent.

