15.4.3 Subject Discontinuation

Subjects may be discontinued from the study for non-treatment-related reasons only when no other option is possible. Reasons for

discontinuation include, but are not necessarily limited to, 1) voluntary withdrawal from the study by the Subject; 2) subject has moved from the area and is determined to be lost to follow-up; 3) Subject is unwilling or unable to cooperate with study requirements (non-compliance with post-operative follow-up visits, etc.).

Prior to discontinuing a Subject, every effort should be made to contact the Subject in an effort either to get the Subject back into compliance with the protocol or to obtain as much follow-up data as possible regarding the Subject's current visual status.

16. Data Reporting

A Case Report Form binder will be provided by the Sponsor for each subject who is enrolled in the study. The appropriate case report form will be completed and signed by the Investigator/examiner at each examination. All case report forms will be completed in a legible manner in ink. Any corrections will be made by drawing a single line through the incorrect entry and initialing and dating the change. Information transferred from the source document will be faxed to the sponsor.

All forms will be reviewed for completeness and evident recording errors will be rectified by contact with the appropriate persons at the clinical site. Corrective and preventative actions will be implemented to avoid repeat errors. Double entry routines will be used to minimize data entry errors, and computerized editing routines will be used to identify unusual data entries for verification prior to statistical analysis. Data analysis will be performed per the statistical analysis plan in Appendix 6.

17. Recording of Data and Retention of Documents

Subject data will be documented in an anonymous fashion and the subject will be identified by the subject enrollment number. If, as an exception, it is necessary for safety or regulatory reasons to identify the subject, the Sponsor or its representative and the Investigator are bound to keep this information confidential.

The Investigator must retain essential documents indefinitely after the completion of the study, unless otherwise notified by the Sponsor. The Investigator agrees to adhere to the document retention procedures when signing the protocol Investigator statement of approval.

Essential documents include but are not limited to the following:

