3 STUDY ENDPOINTS

3.1 Effectiveness Endpoint

3.1.1 Primary Effectiveness Endpoint

The primary effectiveness endpoint identified for this Early Feasibility Study for AccuraSee.

• Proportion of eyes (≥ 50%) able to achieve a stable target refraction within 0.5 D of the intended target. Stability is achieved when there is no change (±0.50 D) in MRSE within two consecutive postoperative visits at 1 month or later visits.

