5 ANALYSIS POPULATIONS

The analyses will include the data of all study eyes where implantation of IOPCL was attempted and/or successful.

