7.4.2 Additional Effectiveness Analyses

The analysis in section 7.4.1 will be repeated using auto-refraction instead of MRSE for an objective understanding of the change in refraction as this study includes patients with underlying pathology with poor BCDVA, which can impact the reliability of MRSE measurements.

All the available monocular uncorrected distance visual acuity at each protocol specified scheduled visit will be presented for the primary eyes. The categorical presentations will include the visual acuity of 20/16 or better, 20/20 or better, 20/25 or better, 20/32 or better, 20/40 or better, 20/50 or better, 20/63 or better, 20/80 or better, and worse than 20/80.

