7.5.2 Successful Delivery of the IOPCL

The analysis of this clinical outcome will be based on the observed data of AccuraSee IOPCL. The number and percent of eyes with successful delivery of the IOPCL will be reported.

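### SAP 7.4.1, the stated primary analysis, does not report the proportion of eyes that are both stable and within 0.5 D of target, and the protocol and SAP name the refraction measure differently

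*SAP*

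**What the plan says.** The protocol (section 2, Primary Effectiveness Endpoint) counts eyes "able to achieve a stable target refraction, (manifest or autorefraction) within 0.5 D of the intended target" and sets the level at 50% or more. Stability means no change beyond ±0.50 D over two consecutive visits at 1 month or later. SAP 3.1.1 has the same endpoint, eyes "able to achieve a stable target refraction within 0.5 D of the intended target", with the same level, but specifies MRSE for stability.

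SAP 7.4.1, the primary analysis, plans for the 4-6 month visit that "MRSE value of the primary eyes will be summarized descriptively by mean, standard deviation, median, minimum, and maximum based on the intended refractive target". It then says that MRSE stability will be calculated. It plans no count of eyes within 0.5 D, no joint count with stability, no percentage and no comparison with 50%.

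SAP 7.4.2, under additional analyses, states: "The analysis in section 7.4.1 will be repeated using auto-refraction instead of MRSE".

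The safety endpoints are handled differently. SAP 7.5.1 to 7.5.3 each plan a count and percentage; for example, 7.5.2 says "The number and percent of eyes with successful delivery of the IOPCL will be reported".

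On the denominator, SAP section 5 includes "all study eyes where implantation of IOPCL was attempted and/or successful", and SAP 6.5 says "All data analyses will be conducted based on available data", without imputation. Protocol section 16 states: "Data analysis will be performed per the statistical analysis plan in Appendix 6".

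**The concern.** An endpoint that is a yes/no result per eye needs an analysis that counts eyes. Five summary statistics of a continuous variable do not fix how many values lie within 0.5 D. A separate stability result does not say whether the stable eyes are the on-target eyes. The planned primary output can therefore leave open whether the study met its own criterion.

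Timing adds some weight. The study is unmasked (SAP 6.3). The 4-6 month results feed an interim analysis (SAP 6.8) and an IDE application (SAP 4). If the count is specified only after those results are seen, the refraction measure, visit pair and denominator could each be chosen with the outcome known.

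The measure wording raises the same issue. SAP 7.4.2 itself notes that poor BCDVA can affect the reliability of MRSE, so manifest refraction and autorefraction may disagree in the same eye. The protocol's wording could be read as letting either one count.

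**Working it through.** The plan has no calculation to reproduce. SAP 6.2 caps the sample at 10 eyes and gives no alpha, power, effect size or SD. The checks below ask whether the outputs of 7.4.1 determine the endpoint. All of them read 7.4.1 in its favour, as error from the intended target, and count an eye as on target if |error| ≤ 0.5 D.

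**1. Same statistics, different counts.** Two constructed sets of 10 errors (D):

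- Set A: four pairs of ±0.625 and one pair of ±1.125. Sum of squares = 8 × 0.390625 + 2 × 1.265625 = 5.65625.
- Set B: one pair of ±0.125, two pairs of ±0.375 and two pairs of ±1.125. Sum of squares = 2 × 0.015625 + 4 × 0.140625 + 4 × 1.265625 = 5.65625.

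Both have mean 0, median 0, minimum −1.125, maximum +1.125 and SD = √(5.65625/9) = 0.793. Eyes within 0.5 D: 0/10 in A and 6/10 in B.

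A second pair also falls on either side of 50%:

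- One pair of ±1, four zeros and two pairs of ±0.625: sum of squares 2 + 4 × 0.390625 = 3.5625.
- One pair of ±1, two pairs of ±0.375 and two pairs of ±0.5: sum of squares 2 + 4 × 0.140625 + 4 × 0.25 = 3.5625.

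Both have mean 0, median 0, range ±1 and SD = √(3.5625/9) = 0.629. The counts are 4/10 and 8/10.

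**2. Separate counts do not give the joint count.** With 6/10 eyes on target and 6/10 stable, the number meeting both lies between max(0, 6 + 6 − 10) = 2 and min(6, 6) = 6. That is 20% to 60%, on both sides of the criterion.

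**3. The denominator can decide.** Suppose 10 eyes are attempted, 8 have data and 4 meet both criteria:

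| Denominator | Result | Exact (Clopper-Pearson) 95% CI |
|---|---|---|
| Eyes with data | 4/8 = 50% | 15.7% to 84.3% |
| All attempted | 4/10 = 40% | 12.2% to 73.8% |

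**4. The measure can decide.** Assume 50% success on each measure. If either one counted, the combined rate would be 50% under full agreement and 1 − 0.5² = 75% under independence. The binomial chance of at least 5/10 successes would be 0.62 and 0.98 respectively.

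**5. Visit pairs.** The scheduled refraction visits at 1 month or later are Form 3 (30-60 days), Form 4 (120-180 days) and Form 5 (330-420 days). At the 4-6 month interim, Form 3 to Form 4 is the only scheduled consecutive pair. At the final analysis, Form 4 to Form 5 also qualifies under the endpoint's own wording.

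**6. Illustration only.** Errors for 10 eyes were drawn from a normal distribution and rounded to 0.125 D, and every 10-eye set sharing the same five statistics was enumerated (4,000 draws per setting). With an assumed mean of 0 or 0.25 D and all eyes stable, pass or fail at 5/10 was left undecided in 1-3% of draws at SD 0.4 D, 27-28% at 0.6 D and 58-65% at 0.9 D. The documents give no mean or SD, so these figures show only that the gap matters little when errors are small and more when the result is near 50%.

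**The case against.** The strongest reply is that almost everything is already specified. SAP 3.1.1 fixes the unit, both 0.5 D limits and the 50% level. SAP 6.1 says categorical variables are summarised by frequencies and percentages. The sponsor will hold every eye's values and can count directly. The study is also descriptive, with no test and no decision rule tied to 50%, and its stated primary objective is positional stability, with refractive change secondary. All of this is correct and lowers the weight. It does not remove the mismatch: 7.4.1 never derives the responder variable that 6.1 would format, and 7.5.1 to 7.5.3 show that the SAP states the count where it plans one.

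Four stronger readings are tempting, and the documents do not support them.

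- A reader might infer that the endpoint is undefined. It is defined in both documents; only the analysis text fails to report it.
- A reader might infer that 7.4.1 summarises raw MRSE. All eyes receive a +3.0 D lens and baseline MRSE may run from −0.5 to +3.0 D, so targets could differ between eyes by up to 3.5 D. But 7.4.1 ties the summary to the intended target, so this reading is disfavoured.
- A reader might infer that only stability from Form 3 to Form 4 can count. The endpoint allows any two consecutive visits at 1 month or later.
- A reader might take the percentages in the illustration as the chance that this trial ends undecided. They rest on assumed distributions and on seeing only the summary statistics.

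On the measure, the referral of analysis to the SAP in protocol section 16 makes MRSE the working choice. It does not clearly hand over the definition of the endpoint, so the two texts still need to agree.

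**Conclusion.** The concern holds. Carried out as written, the stated primary analysis does not estimate the primary effectiveness endpoint, and the autorefraction repeat has the same gap. The constructed sets prove this without any distributional assumption: identical planned statistics are compatible with 0/10 and 6/10, or 4/10 and 8/10, eyes on target. The difference in refraction measure between protocol and SAP is a smaller wording conflict.

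The practical impact is modest. With at most 10 eyes, a result exactly at the criterion, 5/10, would have an exact 95% CI of 18.7% to 81.3%, and neither the interim analysis nor the IDE submission is made conditional on reaching 50%. The point should be fixed because the repair is nearly free. The scenarios for missing eyes and for either-measure success are assumptions chosen to show direction, not forecasts.

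**What to change.** - **SAP 7.4.1:** make the primary result the number and percent of eyes that meet both criteria jointly, set against the 50% level, with an exact 95% CI labelled as descriptive. Keep the five MRSE statistics as supporting, expressed as error from target.
- **Visits:** at the 4-6 month interim, use Form 3 to Form 4. At the final analysis, apply the endpoint's own rule, so that Form 4 to Form 5 also qualifies.
- **Denominator:** report the result over eyes with available data (SAP 6.5) and over all attempted eyes (SAP 5). The sponsor should name in advance which one decides.
- **Measure:** name one deciding refraction measure identically in the protocol endpoint and the SAP (the SAP currently uses MRSE). Report the same joint proportion on the other measure in 7.4.2. Do not let an eye pass on whichever measure succeeds.
- **Timing:** make the change before the 4-6 month outcomes are reviewed. If they have been reviewed, identify and document it as SAP section 1 requires.

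The cost is a few sentences in the SAP and the protocol endpoint, plus one table. It needs no new data, visits or subjects. The reported success rate may be lower than under a reading in which either measure counts.

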7.4.2 Additional Effectiveness Analyses

The analysis in section 7.4.1 will be repeated using auto-refraction instead of MRSE for an objective understanding of the change in refraction as this study includes patients with underlying pathology with poor BCDVA, which can impact the reliability of MRSE measurements.

All the available monocular uncorrected distance visual acuity at each protocol specified scheduled visit will be presented for the primary eyes. The categorical presentations will include the visual acuity of 20/16 or better, 20/20 or better, 20/25 or better, 20/32 or better, 20/40 or better, 20/50 or better, 20/63 or better, 20/80 or better, and worse than 20/80.

7.5 Safety Analyses

The safety population will be used to summarize all safety endpoints. No imputation for the missing values will be performed.

7.5.1 Preservation of BCDVA

The analysis of this clinical outcome will be based on the observed data of AccuraSee IOPCL. The number and percent of IOPCL implanted eyes with a BCDVA loss of 2 or more lines from preoperative will be derived.

Additionally, if needed, data listing or summary will be provided for eyes with a BCDVA loss of ≥ 2 lines from the best BCDVA before the corresponding visits.

7.5.2 Successful Delivery of the IOPCL

The analysis of this clinical outcome will be based on the observed data of AccuraSee IOPCL. The number and percent of eyes with successful delivery of the IOPCL will be reported.

7.5.3 Long-term Adherence and Positional Stability

The analysis of this clinical outcome will be based on the observed data of AccuraSee IOPCL. The number and percent of eyes with minimal change (i.e. \pm 10 microns) between 1-2 months and 4-6- months established and maintained central spacing between the IOPCL and IOL will be reported.

Long-term adherence and positional stability will also be stratified by the surgical technique (e.g., discrete narrow channels or wider sweeping channels).

